Randomization to intervention. The 90 subjects will be allocated to intervention group by a computer-generated adaptive randomization procedure. Because of the adequate but still modest sample size in this study, simple randomization may not provide group equality on variables that affect outcome. Adaptive randomization is better suited to provide group equality if there is some knowledge about what variables affect outcome. The technique of minimization, for example, is one type of adaptive randomization. While this technique may risk subversion or technical error (Hewitt et al, 2006), minimization has been shown to be the best method of ensuring excellent balance between groups for several prognostic factors in small to moderate samples (Scott et al, 2002; Treasure et al, 1998), where blocking and stratification are not effective in small trials. With minimization the treatment allocated to the next participant enrolled in the trial depends on the characteristics of those participants already enrolled to minimize the imbalance across multiple factors. Minimization aims to ensure treatment arms are balanced with respect to predefined patient factors as well as for the number of patients in each group. Simulation studies show that minimization provides better balanced treatment groups when compared to randomization methods such as permuted blocks within strata (Scott et al, 2002). While there is still very little work about factors that predict outcome in PTSD, one study in Veterans showed that combat exposure and pre-deployment preparedness accounted for significant outcome variance using standard exposure-based psychotherapy (Price et al, 2013). There are also data suggesting gender effects of emotional disclosure interventions for PTSD in non-Veteran subjects (Ironson et al, 2013). As such, allocation to group will use an adaptive randomization designed to provide group equality in descending priority on: (1) number in each group, (2) combat exposure, (3) pre-deployment preparedness, and (4) gender. This will be accomplished by using a software program – minim – that will be adapted for the study by the PI and Dr's. [name]. One potential problem of adaptive randomization is added organizational complexity and possible subversion of the randomization. [name] will work with the DA to ensure that the program is clear and easy to use, and they will “sample enroll” 20 Veterans from our program prior to the study to demonstrate ease and effectiveness. The risk of subversion will be controlled by having only one person (DA) manage the minim program and discuss ongoing enrollment statistics with only the statisticians.

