Statistical Analyses, Primary Hypothesis. Prior to the application of any statistical modeling, underlying assumptions and conditions will be examined. Univariate analyses, including tests of distribution assumptions, t-tests, and chi-square tests will be conducted to determine possible significant covariates to be included in further multivariable modeling as well as to investigate efficiency of randomization techniques. All models will be assessed for goodness of fit as well as other diagnostics including assessment for collinearity performed on all covariates chosen for subsequent analyses. Repeated measures analysis of variance will be used to formally test the null hypothesis of no differences in baseline PTSD symptom mean levels and subsequent retest of PTSD symptom mean levels while simultaneously adjusting for any significant covariates. All models will be run accounting for any potential confounders. Analyses will be performed assuming intent to treat and informative loss-to-follow up will be investigated. Additional analyses will be conducted to determine interactions and mediating effects while simultaneously adjusting for other covariates in the model.

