Statistical Analyses, Primary Hypothesis. Prior to the application of any statistical modeling, underlying assumptions and conditions will be examined. Univariate analyses, including tests of distribution assumptions, t-tests, and chi-square tests will be conducted to determine possible significant covariates to be included in further multivariable modeling as well as to investigate efficiency of randomization techniques. All models will be assessed for goodness of fit as well as other diagnostics including assessment for collinearity performed on all covariates chosen for subsequent analyses. Repeated measures analysis of variance will be used to formally test the null hypothesis of no differences in baseline PTSD symptom mean levels and subsequent retest of PTSD symptom mean levels while simultaneously adjusting for any significant covariates. All models will be run accounting for any potential confounders. Analyses will be performed assuming intent to treat and informative loss-to-follow up will be investigated. Additional analyses will be conducted to determine interactions and mediating effects while simultaneously adjusting for other covariates in the model.

Assumptions for Power Calculations. Assumptions are based on interpolated data since primary outcomes in our first ACU study were assessed with the PSS-SR scale and there are no PTSD studies using MIN as the sham. Furthermore, to be consistent with major PTSD research, we will use the CAPS-5 (DSM-5 version) as the primary outcome, and there are as of yet no completed clinical trials using CAPS-5. In our first study, mean pre-treatment PTSD severity score was about 62% of maximum (31.55 of 51). ACU mean decreased 50% - 31.33 (10.1) to 15.65 (13.95) and wait-list mean decreased 9.3% - 30.79 (9.54) to 27.92 (12.33) at post-treatment. We thus assume that subjects will have a baseline mean CAPS-5 score of 50 (10) and a 50% reduction of symptoms and a 38% increased variance (CAPS-5 = 25; SD = 13.8) with ACU. There are sparse data about effects of

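### The covariates of the primary test are left to an undefined significance screen, and two factors minimised on as prognostic appear in no model

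*SAP*

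**What the plan says.** The relevant text is under Statistical Analyses, Primary Hypothesis, in the SAP and, in the same words, in Protocol section IV.

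- Univariate analyses come before modelling: "t-tests, and chi-square tests will be conducted to determine possible significant covariates to be included in further multivariable modeling". The same sentence gives them a second purpose, "as well as to investigate efficiency of randomization techniques".
- The formal test follows: "Repeated measures analysis of variance will be used to formally test the null hypothesis", carried out "while simultaneously adjusting for any significant covariates".
- A further clause is open-ended: "All models will be run accounting for any potential confounders".

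General Approach (both documents) describes a GLMM of CAPS that controls for baseline severity. Age and gender appear there only as examples of demographic characteristics.

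Protocol, Randomization to intervention, minimises on group size, combat exposure, preparedness and gender. It justifies the second and third by a Veteran study in which "combat exposure and pre-deployment preparedness accounted for significant outcome variance using standard exposure-based psychotherapy". Recruitment (Stage II) and Assessment Detail give the two DRRI scales a role in allocation only. Demographic and Other Data lists nine items for matching and analysis, among them combat history but not preparedness, and commits none of them to a model.

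**The concern.** The primary estimate and p-value depend on a selection rule that is not written down, and each reading of it has a cost.

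- **The screen compares arms.** Minimisation exists to make the arms alike on combat exposure and preparedness, so a test for imbalance will almost never pick them. The model then omits the factors the design balanced on. Its standard error still carries variation that the design has removed from the arm difference, so the test is too cautious and loses power.
- **The screen relates covariates to outcome.** The scores enter more often, but outcome data then decide the primary model, and the result varies with the unstated threshold and type of test.

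At stake is some precision that costs almost nothing to recover, and a primary model that could be known before outcomes are seen.

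**Working it through.** **Inputs from the documents:** difference 8.5, pooled SD 14.4 (d = 8.5/14.4 = 0.59), two-sided alpha 0.05, power 80%, N=90, 10% attrition to 40 per arm, and the minimisation factors.

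**Assumptions (not in the documents):** baseline CAPS-5 R-squared 0.20; the two scores add 5, 10 or 20%, and are independent of each other and of baseline; scores cut in thirds for minimisation; 15% women; deterministic minimisation with equal weights; no age effect; an end-treatment linear model stands in for the GLMM.

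**1. The plan's own figure.** Total N = 4 × [SD × (1.960 + 0.842)/difference]² = 4 × (14.4 × 2.802/8.5)² = 90.1. The stated 90 reproduces, as an unadjusted two-group comparison. Unadjusted power is 0.80 at 45 per arm and 0.75 at 40.

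**2. What covariates can buy, by formula.** Power = Φ{8.5/[14.4 × √(1−R²) × √(2/n)] − 1.96}. With n=45 and total covariate R² of 0, 0.10 and 0.20, power is 0.80, 0.84 and 0.88; with n=40 it is 0.75, 0.80 and 0.84. This ignores both baseline adjustment and minimisation, so simulation is needed.

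**3. Simulation.** 20,000 trials per setting. The comparator model is arm + baseline CAPS-5 + gender + age.

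| Added R² of the two scores | 5% | 10% | 20% |
|---|---|---|---|
| Power without scores | 87.0% | 87.5% | 88.4% |
| Power with both prespecified | 88.2% | 90.1% | 94.1% |
| Type I error without | 4.4% | 4.0% | 3.1% |
| Type I error with | 4.8% | 5.1% | 5.2% |

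The gain is 1.2, 2.5 and 5.7 points. Two repeats with fresh code gave 1.5/3.2/5.3 and 1.6/2.2/5.8. With 80 completers it is 1.7/3.5/7.2. In a repeated-measures ANOVA, treated as a change score, it is 1.3/2.8/5.8. At d=0.59, the verdict at p<0.05 differs with versus without the scores in 2.6/3.8/6.3% of trials.

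**4. The two readings of the screen.**
- Arm comparison (t-test, p<0.05): each score enters in under 0.1% of trials, or about 0.3% or less with a 20% random element in the minimisation. Power is as in the row without scores.
- Outcome association (correlation, p<0.05): both scores enter in 8/28/71% of trials, power is 87.7/89.5/93.8% and type I error 4.8-5.0%. With a median-split t-test instead, both enter in only 4/13/41%.

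**5. Combat exposure correlated with baseline CAPS-5.** Holding the marginal R² of the two scores fixed, the gain falls to 0.6/1.5/3.6 points at correlation 0.3 and 0.9/1.2/2.8 at 0.5. At correlation 0.5 in the 10% setting, combat exposure (marginal R² 0.05) has correlation √0.05 = 0.224 with outcome, and baseline alone implies 0.5 × √0.20 = 0.224. Combat exposure then adds nothing beyond baseline, and the whole gain comes from preparedness.

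**6. A weaker baseline covariate with attrition.** With baseline R² 0.10 and 80 completers, power without the scores is about 77-78% at 5-10% added R². At 5%, one run gave 77.4% without the scores and 78.5% with them.

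**The case against.** The strongest reply is that the demonstrated harm is small and rests on R-squared values the documents do not give. At 5-10% added R-squared, only 1 to 3 points of power are at issue, and leaving the factors out pushes type I error below nominal. Baseline severity, the covariate most likely to matter, is already fixed in General Approach. T-tests and chi-square tests, in the same sentence as the check on randomisation, most naturally compare arms and so do not use outcomes. All of this stands, and it limits the weight of the point. It does not supply a rule, and under that very reading the two factors are dropped almost by construction.

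A reader might infer that the open wording inflates type I error. If every covariate subset were tried and the smallest p-value kept, simulated type I error would be 6.3-6.9% over the 16 subsets of age, gender and the two scores; another set-up with eight permitted sets gave 7.8-8.8%. The plan proposes no such practice: it places the univariate analyses before any modelling. These figures are a hypothetical upper bound that depends on the set-up, and they are no prediction for this trial.

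A reader might also infer that N=90 is wrong, or that power is safe whatever is done. Neither follows. The sample size reproduces without covariates, and power falls below 80% in the combination shown in step 6.

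**Conclusion.** The point holds as a low-cost improvement that should be made. The formal test's covariates are chosen by a screen with no threshold, candidates or target, together with an open clause on confounders, and two factors the protocol itself treats as prognostic are in no model. The likely consequence is a mildly conservative test with some power lost. False-positive risk is not shown to rise: a single fixed outcome-based rule also stays near 5%.

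The sizes, about 1-2, 2-3 or 6 points of power, rest on assumed R-squared values and on the simulated form of minimisation. They shrink if combat exposure tracks baseline severity, in which case preparedness may supply nearly all of the gain. That the primary model depends on an unwritten rule is true at any R-squared.

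**What to change.** In General Approach and in Statistical Analyses, Primary Hypothesis, of both documents:

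- State that the primary analysis of CAPS-5 adjusts for baseline CAPS-5, DRRI-2 combat experiences and DRRI-2 preparedness (both as continuous linear terms), gender and age, and that no covariate is selected by significance testing. This replaces the open list of examples.
- If the repeated-measures ANOVA remains the formal test, use the same factors except baseline CAPS-5, which is already part of its outcome.
- Delete the covariate-screening wording, the adjustment for whatever proves significant, and the sentence on potential confounders.
- Keep baseline comparisons between arms descriptive, and label any other covariate set a sensitivity analysis.

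Whether the GLMM or the ANOVA is primary, and how the fidelity and expectancy interactions are handled, are separate questions that this change leaves open.

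The cost is wording in two documents and about two model degrees of freedom. The DRRI scales are already collected before randomisation, so no new data are needed.
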